1.9 Research Instrument

Cryotherapy was performed using a glove containing crushed ice applied to the perineal region for 20 minutes, initiated up to 12 hours postpartum. Patients were assessed before application, immediately after application, and again 24 hours after application. A glove containing crushed ice was chosen due to its anatomical fit and ability to cover the entire perineal region. Francisco et al. (2013) suggest that surface ice has the ability to decrease skin and intramuscular tissue temperature. Compared to other cryotherapy techniques such as gel and frozen pea bags, the ice bag is the most adopted technique for perineal pain relief. The application time aligns with the study by Beleza et al. (2016), indicating that 20

minutes is sufficient time to cause reduction and relief of pain in study participants.

Low-Level Laser Therapy (LLLT), like cryotherapy, was applied up to 12 hours postpartum, targeting the lesion area. Red light radiation was applied at 3 joules, punctually, with a non-contact technique, maintaining a 2 cm distance between points. Subsequently, infrared laser was applied using the conventional contact technique around the lesion extension, punctually, at 6 joules, also maintaining a 2 cm distance between points.

The LLLT device used was the DMC Therapy EC, portable, with a li-ion battery. The red laser had a wavelength of 660nm (\pm 10 nm) and an emitter power of 100 mW (\pm 20%). The infrared laser had a wavelength of 808 nm (\pm 10) and an emitter power of 100 mW (\pm 20%).

The use of infrared radiation is associated with being a superficial thermal agent, used to reduce pain and stiffness, favoring the regeneration of soft tissue injuries and skin problems. (KITCHEN; PARTIDGE, 1991; MICHLOVITZ, 1986).

LLLT application should be punctual, applying firm pressure to the tissue area to be treated, resulting in higher levels of tissue light flow. This application is characterized by the conventional contact technique, whereas the non-contact technique involves application around the wound margins. These combined techniques ensure better application and absorption of radiation. Application should occur around the circumference of the lesion, approximately 1-2 cm from its margins, with application points spaced 2-3 cm apart. (KITCHEN, 2003).

The two most common means of LLLT application are characterized by a wavelength of approximately 633 nm (red light) and 904 nm (infrared), capable of inducing mitochondrial activity and initiating reactions at the cellular membrane level, respectively. (KITCHEN, 2003).

Patients underwent evaluation using a questionnaire, the Patient Assessment Form, developed by the researcher. Pain and edema were evaluated using the Visual Analog Scale (VAS), McGill Pain Questionnaire (MPQ), and REEDA scale before, immediately after, and 24 hours after therapy application.

Pain was assessed on a scale of 0 to 10 using the VAS, with 0 indicating no pain and 10 indicating maximum pain intensity.

The McGill Pain Questionnaire (MPQ) was used to assess other characteristics of pain, not just intensity. This questionnaire captures quantitative measures of pain, with established validity and reliability, allowing for discrimination of various pain components. The questionnaire consists of 20 items, or groups, with each group containing several words from which the patient selects the one that best identifies their pain, selecting only one word per group. The groups are subdivided into sensory responses to painful experience (Groups 1-10), affective responses (Groups 11-15), evaluative responses (Group 16), and miscellaneous

(Groups 17-20). The questionnaire takes 3 to 4 minutes to complete. (PIMENTA; TEIXEIRA, 1996).

Edema was evaluated using the REEDA scale, which assesses inflammatory processes and tissue recovery following perineal trauma. Five scar healing items are evaluated: redness, swelling, bruising, discharge, and wound edge approximation (coaptation). A score of zero to three is assigned to each item evaluated by the assessing professional, with a maximum score of 15 indicating the worst perineal healing. (ALVARENGA et al., 2015).

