1.4 Data Collection

The data collection was performed through Physiotherapeutic Assessment (APPENDIX A), and the data were stored in an Excel spreadsheet. **Amostragem e amostra**

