1.4.3 Sample

1.5 The sample consisted of women admitted to a public hospital in the Vale do Sinos region who underwent vaginal delivery and experienced some complication during delivery, such as episiotomy or first- or second-degree laceration. The sample size calculation was based on studies by Santos et al. (2012) and Morais et al. (2016), using the StatCalc – Sample Size and Power tool in the Epilnfo software.

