1.7 Operational Definition of Variables

1.8 1.7.1 Study Factor

The comparison of two non-pharmacological techniques used for pain and edema relief, performed in immediate postpartum up to 12 hours, being evaluated

before the application of the techniques, immediately after, and reevaluated after 24 hours.

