1.7.2 Main Outcome

The idea of using non-pharmacological techniques in immediate postpartum is to reduce pain, edema, and inflammatory processes, causing greater comfort and better recovery in the puerperium.

a) Primary Outcome

- Compare the two techniques to assess which is more effective in relieving pain and/or edema in immediate postpartum up to 12 hours.

b) Secondary Outcome

- Reduce pain and/or edema and promote healing in immediate postpartum.

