2 DATA COLLECTION PROTOCOL

Step 1: Contact and presentation to the head responsible of the Obstetrics Center and then to the coordinating nurse of the Obstetrics department at the Municipal Hospital of Novo Hamburgo. After introducing myself and presenting the project, I provided my contact information and made myself available to be called whenever there was a patient who fit the sample profile of this study, taking responsibility for its implementation.

Step 2: After signing the Informed Consent Form (ICF), a physiotherapeutic assessment was conducted with the patient, as per the form in Appendix B.

Step 3: The patient underwent random selection to determine which intervention group she would be assigned to.

Step 4: After group assignment, within 12 hours post-vaginal delivery, the patient underwent an assessment of edema and pain using available scales (Appendices A, B, and C).

Step 5: The randomly determined intervention, either cryotherapy or laser therapy, was administered within 12 hours post-immediate vaginal delivery.

Following the application described in this study, the patient was immediately reassessed for pain using the VAS scale.

Step 6: The patient was reassessed 24 hours post-delivery, and pain and edema scales were applied. After this period, the patient was discharged.

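### Pre-treatment VAS pain is scored in every woman, but the plan gives it no role in the laser-versus-cryotherapy comparison and takes it only after the open draw

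*Combined protocol and SAP*

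**What the plan says.** The primary outcome in 1.7.2 is to "Compare the two techniques to assess which is more effective in relieving pain and/or edema in immediate postpartum up to 12 hours". No summary measure is attached to it: no post-treatment score, change score or adjusted difference.

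The pre-treatment score is clearly part of the design. Section 1.7.1 has the women evaluated "before the application of the techniques, immediately after, and reevaluated after 24 hours", and section 1.9 repeats this for the VAS, the McGill questionnaire and the "REEDA scale before, immediately after, and 24 hours after therapy application". On the VAS, "Pain was assessed on a scale of 0 to 10 using the VAS".

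The numbered steps in section 2 fix the order. The lot is drawn at Step 3. Step 4 then reads: "After group assignment, within 12 hours post-vaginal delivery, the patient underwent an assessment of edema and pain using available scales". After treatment, "the patient was immediately reassessed for pain using the VAS scale" (Step 5). The study design section describes the draw as open: the woman herself takes a slip that names the treatment. No blinding is described.

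On analysis, section 1.4 says only that "the data were stored in an Excel spreadsheet". The sample size is said to have been derived "using the StatCalc – Sample Size and Power tool in the Epilnfo software" from two earlier studies, but no number of women, SD, effect size, alpha or power is given.

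**The concern.** Starting pain is usually the most useful covariate in a pain trial, and here it is collected from everyone. A plan that asks which technique relieves pain better, holds scores from before and after treatment, and names no estimator leaves three analyses open: post-treatment scores alone, change from baseline, and post-treatment scores adjusted for baseline. They differ in precision and can differ in result. If the choice is made after the data are seen, the reader cannot tell whether the result influenced it.

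The order of Steps 3 and 4 adds a second problem. A self-reported score given by a woman who knows which treatment she is about to receive may be shifted by that knowledge. Such a baseline is a weaker covariate than one taken before the draw.

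**Working it through.** There is no stated sample size, power or analysis to reproduce. The check therefore compares the three candidate analyses.

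**Inputs.** From the documents: VAS from 0 to 10, one score before treatment and one immediately after (1.9; Steps 4 and 5). Assumed, because the documents give no value: 1:1 allocation, equal SDs before and after, VAS treated as continuous, and baseline/follow-up correlation r from 0.2 to 0.7.

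**Precision.** Large-sample variance of the arm difference, relative to post-treatment scores alone (= 1):

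- ANCOVA: 1 − r². At r = 0.5: 1 − 0.25 = 0.75.
- Change score: 2(1 − r). At r = 0.5: 2 × 0.5 = 1.00.

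Power is Φ((1.96 + 0.842)/√V − 1.96), where V is the relative variance. It starts from an assumed 80% for the post-only analysis at two-sided 5%.

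| r (assumed) | ANCOVA variance | Change variance | Post-only ÷ ANCOVA | Change ÷ ANCOVA | Power, ANCOVA | Power, change |
|---|---|---|---|---|---|---|
| 0.2 | 0.96 | 1.60 | 1.04 | 1.67 | 81.6% | 60.1% |
| 0.3 | 0.91 | 1.40 | 1.10 | 1.54 | 83.6% | 65.8% |
| 0.5 | 0.75 | 1.00 | 1.33 | 1.33 | 89.9% | 80.0% |
| 0.7 | 0.51 | 0.60 | 1.96 | 1.18 | 97.5% | 95.1% |

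The ratio columns read as the relative number of women needed for equal precision. In confidence interval width, leaving baseline out costs 1/√0.96 − 1 = 2% at r = 0.2 and 1/√0.51 − 1 = 40% at r = 0.7.

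**Cost of adjusting.** With an assumed 20 women per arm, estimating one slope inflates the variance by about 1 + 1/(40 − 4) = 1.028. ANCOVA then beats post-only once (1 − r²) × 1.028 < 1, that is, once r exceeds about 0.16.

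**Chance imbalance.** With the same assumed 20 per arm, the baseline difference D has a 95% range of ±1.96 × √(2/20) = ±0.62 SD. With equal SDs, D moves a post-only contrast by rD and a change-score contrast by (r − 1)D. For D = 0.62 SD and r = 0.5, that is +0.31 SD and −0.31 SD. ANCOVA removes this shift.

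**Baseline taken after the draw.** If knowing the allocation moved baseline scores in one arm by d, with no change in true pain, the ANCOVA contrast would move by about −r × d (slope r with equal SDs) and a change-score contrast by −d. A post-only contrast would not move. The documents give no basis for a value of d.

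**Time points.** VAS immediately after treatment appears in both 1.9 and Step 5. The last visit does not agree: 1.9 counts 24 hours from application, Step 6 counts 24 hours from delivery. Treatment may start up to 12 hours after delivery, so the two clocks can differ by up to 12 hours (24 versus 24 + 12 = 36 hours after delivery).

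**The case against.** The strongest objection is that no imprecise analysis has been specified. A reader might infer that the plan commits to change scores or unadjusted comparisons, so that the primary answer is already less precise. The documents do not support that: the wording about relieving pain defines no estimator, and adjustment is not ruled out. This stands, and it makes the loss conditional.

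Other limits also stand:

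- A change score does use the baseline. At r = 0.7 its variance is 0.60, close to the 0.51 of ANCOVA and well below post-only.
- A reader might take the ±0.62 SD as bias in the result or as extra false positives. Only about r times a chance imbalance reaches a post-only contrast (0.19 SD at r = 0.3, 0.43 SD at r = 0.7). Under randomisation that variation is already within the unadjusted standard error.
- The trial may or may not be small. Twenty per arm is an illustration, and every size above rests on assumed correlations.
- The missing baseline role is one part of a wider absence of analysis text.

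None of this gives the collected score a role. It remains a specific omission that can be repaired separately from the rest.

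**Conclusion.** The point holds in conditional form. Pre-treatment VAS is collected from every woman and has no stated role in the primary comparison. If baseline is ignored or raw change is used, precision is lost. For assumed r of 0.3, 0.5 and 0.7 with equal SDs, the analysis would need 10%, 33% and 96% more women than ANCOVA if it used post scores alone, and 54%, 33% and 18% more if it used change scores. At r = 0.2 the gain over post scores is only 4%. The documents cannot narrow this range.

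The order of Steps 3 and 4 is a fact of the plan. A reader might infer that the baseline scores are biased. The documents show only that the opportunity exists, through an open draw and a self-reported score with no blinding described, and not that any shift occurred.

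This is a worthwhile improvement at little cost. It is not a flaw that invalidates the comparison.

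**What to change.** After 1.7.2, add a paragraph along these lines: *The primary pain estimate is the laser-minus-cryotherapy difference in VAS immediately after treatment, from a linear model with arm and pre-treatment VAS, reported with a 95% confidence interval. VAS at the later visit is secondary and is analysed with the same baseline adjustment.* The immediate score is the one that best fits the 12-hour limit in the primary outcome, and it is described consistently in 1.9 and Step 5.

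Before the secondary analysis is fixed, reconcile the two definitions of the last visit in 1.9 and Step 6. The paragraph covers pain only. The edema part of the primary outcome needs its own statement, and 1.9 and Step 5 must first agree on whether REEDA is scored immediately after treatment.

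Move the pre-treatment pain scoring ahead of the draw by swapping Steps 3 and 4. If recruitment is complete, as the mostly past tense suggests, state the post-allocation baseline as a limitation and show the unadjusted post-treatment difference beside the adjusted one, since it does not depend on that score. If outcome data have already been examined by arm, label the model as chosen afterwards.

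The cost is one paragraph, one model degree of freedom and, where still possible, a reordering of two existing steps. No extra visits or women are needed.

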2 DATA COLLECTION PROTOCOL

Step 1: Contact and presentation to the head responsible of the Obstetrics Center and then to the coordinating nurse of the Obstetrics department at the Municipal Hospital of Novo Hamburgo. After introducing myself and presenting the project, I provided my contact information and made myself available to be called whenever there was a patient who fit the sample profile of this study, taking responsibility for its implementation.

Step 2: After signing the Informed Consent Form (ICF), a physiotherapeutic assessment was conducted with the patient, as per the form in Appendix B.

Step 3: The patient underwent random selection to determine which intervention group she would be assigned to.

Step 4: After group assignment, within 12 hours post-vaginal delivery, the patient underwent an assessment of edema and pain using available scales (Appendices A, B, and C).

Step 5: The randomly determined intervention, either cryotherapy or laser therapy, was administered within 12 hours post-immediate vaginal delivery.

Following the application described in this study, the patient was immediately reassessed for pain using the VAS scale.

Step 6: The patient was reassessed 24 hours post-delivery, and pain and edema scales were applied. After this period, the patient was discharged.

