1.1 Delineamento do estudo

1.2 This is a randomized clinical trial aimed at comparing the effects of cryotherapy and low-level laser therapy on postpartum women up to 24 hours after delivery. The control group will receive cryotherapy (CG), and the intervention group will receive low-level laser therapy (GL). This study was randomized by drawing lots, where there was a paper in a black bag with "LLT" or "cryotherapy" written on it, and the patient would draw the paper from the bag to select the treatment to be applied. A randomized clinical trial is the gold standard for an experimental study or clinical trial, allowing the evaluation and demonstration of cause-and-effect relationships between various independent and dependent variables (SHARMA; SRIVASTAV; SAMUEL, 2020). Randomization by randomly generated numbers by computer, tables, coin toss,

and dice games is considered appropriate (SOUZA; SOUSA; SANTOS JR. et al, 2019).

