APPENDIX A - PHYSIOTHERAPEUTIC EVALUATION FORM

PHYSIOTHERAPEUTIC EVALUATION FORM

NAME:

DATE OF BIRTH: _____ AGE:

CITY OF RESIDENCE:

PHONE:

EDUCATION:

OCCUPATION:

MARITAL STATUS:

RELATIONSHIP DURATION:

WEIGHT: _____ HEIGHT: _____ BMI: _____

NUMBER OF PREGNANCIES:

NUMBER OF VAGINAL DELIVERIES:

NUMBER OF CESAREAN SECTIONS:

SMOKER: () YES () NO

ALCOHOL: () YES () NO

DRUGS: () YES () NO

PREVIOUS ILLNESSES:

ILLNESSES DURING PREGNANCY:

GYNECOLOGICAL SURGERIES: ______ WHICH:

ASSOCIATED MEDICATIONS:

VAGINAL DELIVERY: () EPISIOTOMY () EPISIOTOMY + FORCEPS

() EPISIOTOMY + 1ST DEGREE LACERATION

() 1ST DEGREE LACERATION () 2ND DEGREE LACERATION

MEDICATIONS USED POSTPARTUM:

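### The only documented pre-treatment pain and edema scores are taken after the patient has drawn her treatment, so the baseline is not a pre-allocation measure

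*Combined protocol and SAP*

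**What the plan says.** Section 2 (Data Collection Protocol) sets the order of events. Step 2 is consent followed by a physiotherapeutic assessment. Step 3 is the draw: "The patient underwent random selection to determine which intervention group she would be assigned to". Step 4 holds the scales: "After group assignment, within 12 hours post-vaginal delivery, the patient underwent an assessment of edema and pain using available scales". Step 5 is treatment.

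The study design text (sections 1.1 and 1.2) describes the draw itself. Papers in a bag have one of the two treatments "written on it, and the patient would draw the paper from the bag to select the treatment to be applied".

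Sections 1.7.1 and 1.9 say that the scales were given before the techniques were applied. They do not say whether that was before or after the draw.

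On scoring, section 1.9 says of REEDA: "A score of zero to three is assigned to each item evaluated by the assessing professional". Section 1.3 says that the researcher applied the treatments. No blinding is described.

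The appendix labels conflict. Step 2 says that "a physiotherapeutic assessment was conducted with the patient, as per the form in Appendix B", but section 1.4 and the form's own title, "APPENDIX A - PHYSIOTHERAPEUTIC EVALUATION FORM", make the physiotherapeutic form Appendix A. Step 4 cites Appendices A, B and C together as the scales.

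**The concern.** A baseline score is normally taken before allocation, so that nothing about the assigned arm can influence it. Here the documented order is the reverse. VAS and MPQ are self-reported, and the patient has just read the name of her treatment. A woman who hoped for the other treatment, or who expects much from the one she drew, may rate her pain differently.

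Two uses of the baseline are exposed:

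- **Effect estimate.** Section 1.7.2 speaks of relieving and reducing pain and edema, which invites an analysis of change from baseline, though none is named. A difference between arms in baseline reporting would then become part of the estimated effect.
- **Comparability check.** Readers will look at baseline scores to judge whether drawing lots gave similar groups. Scores taken after the draw mix chance imbalance with any effect of knowing the arm.

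**Working it through.** **Order of events.** Steps 3 and 4 read with the study design text give: draw, arm known to the patient, scales, treatment. The statements in sections 1.7.1 and 1.9 place the scales ahead of treatment, which is true of Step 4 and does not move them ahead of the draw. No section describes a pain or edema score before the draw. The only assessment placed there is Step 2, and the Appendix A form has no VAS, MPQ or REEDA field. Appendices B and C are not in the text available for review, so the conflicting labels leave open that a pre-draw score exists.

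**Size.** The plan has no figure to reproduce. It gives no SD, pre-post correlation or analysis method, so what follows rests on assumptions. Let *b* be the between-arm shift in reporting at baseline caused by knowing the arm, *f* the same shift at follow-up, and *r* the slope of follow-up on baseline within arms (equal to the correlation when the SDs are equal). Assume no true effect.

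- Change score: bias = *f* − *b*
- ANCOVA: bias = *f* − *r* × *b*
- Follow-up only: bias = *f*
- Pre-draw baseline, any of the three: bias = *f*

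With *b* = 0.5 VAS points and *r* from 0.3 to 0.7, *r* × *b* runs from 0.15 to 0.35:

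| Follow-up shift *f* | Change score | ANCOVA (*r* = 0.3 to 0.7) | Follow-up only | Any analysis, pre-draw baseline |
|---|---|---|---|---|
| −0.50 | −1.00 | −0.65 to −0.85 | −0.50 | −0.50 |
| −0.25 | −0.75 | −0.40 to −0.60 | −0.25 | −0.25 |
| 0 | −0.50 | −0.15 to −0.35 | 0 | 0 |
| +0.25 | −0.25 | +0.10 to −0.10 | +0.25 | +0.25 |
| +0.50 | 0 | +0.35 to +0.15 | +0.50 | +0.50 |

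These biases do not depend on sample size or SD.

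**When a pre-draw baseline helps.** For change scores it gives the smaller bias when (*f* − *b*)² > *f*², which for *b* > 0 means *f* < *b*/2, here below 0.25. For ANCOVA the condition is *f* < *r* × *b*/2, here below 0.075 to 0.175. So it helps when the shift fades or reverses by follow-up. When the shift persists it makes both analyses worse, because a post-draw baseline carries the same shift and partly or wholly cancels it. The follow-up-only comparison is the same either way.

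**The case against.** The strongest reply is that the illustration does not favour reordering the steps. Ice and laser are plainly different to the patient and no blinding is described, so a reporting shift that persists to follow-up is at least as plausible as one that fades. In the rows with *f* at +0.25 or +0.50, moving the scales ahead of the draw leaves the size of the change-score bias unchanged or makes it larger, and it makes ANCOVA worse. This stands, and it is why the point cannot claim a smaller net bias. Opposite-sign shifts cut the other way, and the documents do not say which case applies.

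It can also be said that the harm is conditional: if only follow-up scores are compared, this channel is absent. That stands too. And because most of the text describes conduct in the past tense, reordering may no longer be possible. The future tense for the two arms in the study design section leaves the state of enrolment unclear.

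Stronger readings are tempting but unsupported:

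- A reader might infer that the baseline scores *are* biased. Nothing in the documents shows that a shift occurred, or its direction.
- A reader might take the follow-up-only comparison as the unbiased reference. It carries *f* in full.
- A reader might conclude that the REEDA scorer knew the arm. That is an inference from who applied the treatments and from the absence of any described blinding. Section 1.9 refers only to the assessing professional.
- A reader might conclude that no pre-draw score exists. The appendix labels do not allow that to be settled.

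**Conclusion.** The ordering point holds. The only documented pre-treatment pain and edema scales follow a draw that tells the patient her arm. Baseline VAS and MPQ are therefore open to an avoidable influence, and REEDA may be. Under the assumptions above, the bias from the combined baseline and follow-up shifts lies between −1.00 and 0 VAS points for change scores and between −0.85 and +0.35 for ANCOVA. These ranges follow from the chosen *b*, *f* and *r* and do not estimate what happened. A pre-draw baseline removes one channel and restores a clean comparability check. It does not remove open-label bias at follow-up.

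Severity is minor. Confidence is medium, because Step 2 could conceal a pre-draw score and the analysis is not stated.

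**What to change.** State whether enrolment is closed, then:

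**Women still to be enrolled, if any.** Reorder Steps 3 and 4 so that VAS, MPQ and REEDA are recorded, with clock time, after consent and before the draw. Flag in the dataset which order each woman followed. The scales are moved, not added, and Step 2 already places an assessment at that point. The downside is a possibly longer interval from baseline to treatment if Steps 2 to 5 are not one contact, which is why the clock time is needed.

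**Data already collected.**

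1. Reconcile the assessment schedule. Step 5 repeats only VAS immediately after treatment, while section 1.9 repeats all three scales. Step 6 counts 24 hours from delivery, while section 1.9 counts from application. As treatment may start up to 12 hours postpartum, the two anchors can differ by up to 12 hours.
2. State in the report that baseline was taken after allocation and unblinded.
3. Show baseline VAS, MPQ and REEDA by arm. Note that similar values do not exclude a shift and that different values may be chance.
4. Beside any change-score or baseline-adjusted result, report the follow-up-only comparison as a sensitivity analysis: VAS immediately after treatment, and VAS, MPQ and REEDA at the 24-hour assessment. If the analyses disagree, report all of them and treat none as the unbiased reference.
5. Reconcile the Appendix A, B and C labels. If a pre-draw pain or edema score exists, report it as the baseline.

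The cost is a disclosure sentence, a baseline table, the extra comparisons and corrections to the text. The follow-up-only comparison is less precise than ANCOVA: its standard error is 1/√(1 − *r*²) times as large, or 1.05, 1.15 and 1.40 times at *r* = 0.3, 0.5 and 0.7.
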